11.3 Other Safety Endpoints

The ophthalmic assessments for safety include IOP measurement using Goldmann applanation tonometry, ETDRS assessment of best corrected visual acuity by the Pinhole method, Slit Lamp biomicroscopy assessment of the relevant signs of inflammation, and dilated indirect ophthalmoscopy assessment.

11.3.1 Intraocular Pressure

IOP assessments will be performed from Screening through EOS for the study eye. IOP assessments will be performed at Screening and EOS for the non-study eye.

For the study eye, the IOP data and change from baseline (POD1 pre-dose) at each post-surgery scheduled visit through EOS will be summarized by treatment group using descriptive statistics, including 95% CI for the mean of change from baseline. The IOP change from Screening to each

scheduled post-surgery visit through EOS for the study eye will be summarized to evaluate any potential impact from IOP lowering medication use on the surgery day (Day 0). A box and whisker plot will be presented for the IOP change from baseline through EOS and for the IOP change from Screening through EOS for the study eye. The IOP change from POD15 to POD22 for non-rescued subjects who complete the study will be summarized for the study eye.

The IOP increase from baseline and increase from Screening will be categorized as ≤ 0 , 1-5, 6-10, > 10 (mmHg). The number and percentage of subjects in each category will be tabulated at each post-surgery visit for the study eye. In addition, subjects with an IOP ≥ 21 mmHg and an increase > 10 mmHg from baseline, and subjects with an IOP > 30 mmHg at any time following initiation of study drug will be summarized and listed for the study eye.

The IOP data collected after taking rescue medication will be excluded from the summary tables and plots for the study eye.

The IOP data at Screening and EOS, and change from Screening to EOS for the non-study eye will be summarized using descriptive statistics.

All IOP data, including data collected after taking rescue medication, will be presented in a data listing.

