8.1.1 Subjects who are Randomized

- An AE related to cataract surgery will be recorded in the Surgical AE log table in the source documents and in the eCRF.
- AEs occurring prior to study drug administration will be recorded in the source documents only.
- AEs occurring from the start of study drug administration will be reported in the source documents and eCRF.
- Rescued subjects are considered to be treatment failures, and being rescued itself is not considered to be an AE.
- Adverse events occurring in rescued subjects will be reported in the source documents and eCRF.
- An IOP > 30 mmHg after Randomization will be reported as an AE in the source documents and eCRF.
- An IOP ≥ 21 mmHg AND an IOP increase > 10 mmHg from pre-dose baseline will be reported as an AE in the source documents and eCRF.
- Serious Adverse Events will be collected from the time of signature of the informed consent form and reported in the source documents and eCRF.

The term “severe” is used to describe the intensity of an AE; the event itself could be of relatively minor clinical significance (e.g., ‘severe’ headache). This is not the same as “serious”. Seriousness of AEs is based on the outcome of an AE and usually associated with events that pose a threat to a subject’s life or functioning.

A Treatment Emergent Adverse Event (TEAE) will be defined as any AE that occurs from the start of study drug administration through Visit 6 (POD22).

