10.3.3 Analysis of Safety

Analysis of safety data will be performed for all subjects in the Safety Population.

Adverse events will be coded using Medical Dictionary for Regulatory Activities (MedDRA) and classified by system organ class and preferred terms. Adverse events will be summarized by total number of TEAEs, number of subjects reporting TEAEs, ocular TEAEs (affecting the study eye and/or the non-study eye and/or both eyes, when appropriate), non-ocular TEAEs, SAEs, serious and unexpected suspected adverse reaction (SUSARs), discontinuing study drug due to an AE, by relationship to study drug and/or ocular surgical procedure, and by severity.

The IOP data for both eyes will be summarized at screening, Visit 6 (POD22)/Early Termination (Withdrawal) visit and change from screening. The observed IOP data and change-from-baseline (POD1) for the study eye will be summarized at each post-surgery visit.

The data for slit lamp biomicroscopy examination endpoints will be summarized at each visit. The summary of change-from-baseline at each post-surgery visit will be presented for the study eye.

Dilated indirect ophthalmoscopic examination findings for the study and non-study eye will be summarized at screening and Visit 6 (POD22)/Early Termination (Withdrawal).

Visual Acuity data will be summarized at each visit. The summary of change-from-baseline at each post-surgery visit will be presented for the study eye.

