4. SAMPLE SIZE CONSIDERATION

The assumption for the sample size determination was estimated using the Package Inserts of Durezol®, Lotemax® and Inveltys® and results from the APP13007 Phase 2 study (CPN-201). The sample size for ACC count primary efficacy endpoint is based on the assumption of 26% of subjects in APP13007 group with ACC Count = 0 at POD8 and maintained through POD15 and 12% of subjects in the matching vehicle placebo group. The two-group Chi-square test, with a two-sided significance level of 5% and 92% power, requires 175 subjects per treatment group to detect the difference between APP13007 and placebo.

The same sample size using the assumption of 57% of subjects with Ocular Pain Grade = 0 at POD4 and maintained through POD15 in APP13007 group and 38% of subjects in the placebo group will provide 95% power to detect the treatment difference.

With an estimated 5% dropout rate, this study will randomize approximately 185 subjects per treatment group for a total of approximately 370 subjects.

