11. SAFETY ANALYSES

The extent of exposure and all safety endpoints will be summarized using the Safety population. For all safety endpoints, the observed data and scheduled visits will be used for summary statistics. No imputation of missing data will be employed.

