11.3.2 Best Corrected Visual Acuity

Since the BCVA endpoint will also be assessed for efficacy, this endpoint has been described in the [Section 10.2.1](#). The assessments for the study eye will be performed from Screening through EOS for safety evaluation. The assessment for the non-study eye will be performed at Screening and EOS.

The BCVA LogMAR scores and change from baseline (POD1 pre-dose) will be summarized descriptively by treatment group at each post-surgery scheduled visit through EOS for the study eye. The BCVA base LogMAR scores change from baseline will be classified as ≤ 0 , $0 < - < 0.2$ and ≥ 0.2 , which are equivalent to ≤ 0 line (visual acuity improved), $0 < - < 2$ lines, and ≥ 2 lines (visual acuity worsened). The number and percentage of subjects in each category will be tabulated at each post-surgery scheduled visit for the study eye.

The BCVA scores collected after taking rescue medication will be excluded from the summary tables for the study eye.

The BCVA LogMAR scores at Screening and EOS, and change from Screening to EOS for the non-study eye will be summarized using descriptive statistics.

All BCVA data, including data collected after taking rescue medication, will be presented in a listing.

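### Safety summaries of IOP and BCVA omit readings after rescue, and the SAP leaves unclear whether its any-time raised-IOP count includes post-rescue and unscheduled readings

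*SAP*

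**What the plan says.** Three SAP rules limit which safety readings are summarized.

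- SAP 11, for all safety endpoints: "the observed data and scheduled visits will be used for summary statistics".
- SAP 11.3.1: "The IOP data collected after taking rescue medication will be excluded from the summary tables and plots for the study eye".
- SAP 11.3.2: "The BCVA scores collected after taking rescue medication will be excluded from the summary tables for the study eye".

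SAP 11.3.1 also promises to summarize and list subjects with IOP > 30 mmHg at any time after study drug starts, alongside those with IOP >= 21 mmHg and a rise > 10 mmHg from baseline. The exclusion sentence comes directly after this promise. All IOP and BCVA data, including post-rescue data, go into listings.

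Protocol 10.3.3 says: "The observed IOP data and change-from-baseline (POD1) for the study eye will be summarized at each post-surgery visit". It plans visual acuity at each visit too, uses the Safety Population, and mentions no rescue exclusion. Protocol 9.4.2 keeps rescued subjects in the study through POD22, so the excluded readings will be collected.

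Protocol 8.1.1 makes both IOP thresholds reportable AEs and adds: "Adverse events occurring in rescued subjects will be reported in the source documents and eCRF". Under SAP 11.2, TEAEs run from first dose to end of study with no cut at rescue.

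**The concern.** IOP increase is a listed corticosteroid class risk (protocol 1.5.1.4 and Table 2). Rescue happens after randomization and is driven by lack of efficacy (protocol 9.4.1), so if the drug works it will probably be less common on APP13007. Removing readings after rescue then leaves two arms selected differently by response. Rescue may also be related to IOP itself: protocol 1.2.2 lists raised IOP among the possible consequences of poorly managed inflammation.

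The more concrete problem lies inside SAP 11.3.1. An any-time count and a blanket exclusion from the summary tables stand next to each other, under a general rule restricting summaries to scheduled visits, and nothing says which takes precedence. Two programmers could produce different counts for the main raised-IOP summary, and one of those counts could disagree with the TEAE table.

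**Working it through.** **The plan's own figures.** The documents give no rescue rate and no raised-IOP rate, so only the arm size can be reproduced. The inputs are in SAP 4: "26% of subjects in APP13007 group with ACC Count = 0 at POD8 and maintained through POD15", "12% of subjects in the matching vehicle placebo group", and a test that, "with a two-sided significance level of 5% and 92% power, requires 175 subjects per treatment group".

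- n = [1.960 × √(2 × 0.19 × 0.81) + 1.405 × √(0.26 × 0.74 + 0.12 × 0.88)]² / 0.14² = 175.4, or 176 rounded up, against 175 stated.
- Power at 175 per arm is 91.9% for ACC (stated 92%) and 94.8% for pain, 57% vs 38% (stated 95%).
- 175 / 0.95 = 184.2, or 185 per arm.

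These agree with the plan. Only the 185 is used below.

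**Where a first threshold IOP reading appears, by the text.**

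| Reading | By-visit IOP tables | Any-time summary | TEAE tables | Listing |
|---|---|---|---|---|
| Scheduled, before rescue | in | in | in | in |
| Unscheduled, before rescue | out (SAP 11) | unclear | in | in |
| Scheduled, after rescue | out (SAP 11.3.1) | unclear | in | in |
| Unscheduled, after rescue | out (both rules) | unclear | in | in |

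The three unclear cells are the defect. BCVA has a thinner backstop than IOP. No numeric acuity threshold is a reportable AE; protocol 7.3.1.1 asks only that clinically relevant deterioration be recorded. SAP 6.4.2 also excludes post-rescue assessments from the efficacy analyses. SAP 11.3.3 puts no rescue exclusion on slit-lamp grades, so safety tables at the same visit can rest on different subjects.

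**Subjects affected.** Count = 185 × rescue rate; all rates are assumptions.

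| Rescue, APP13007 / placebo | Subjects losing later readings |
|---|---|
| 2% / 10% | 3.7 / 18.5 |
| 5% / 20% | 9.3 / 37 |
| 10% / 40% | 18.5 / 74 |

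These subjects keep their pre-rescue readings. Anyone rescued at POD15 completes the POD15 assessments first (protocol 9.4.2) and so loses only later readings.

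**Threshold subjects missing under the literal reading.** Take 5% / 20% rescue and assume a fraction q of 1% to 5% of rescued subjects have their first threshold reading after rescue.

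- Expected number on APP13007: 9.25 × 0.01 to 9.25 × 0.05 = 0.1 to 0.5.
- Expected number on placebo: 37 × 0.01 to 37 × 0.05 = 0.4 to 1.9.
- Chance of at least one in the trial (m = 9 + 37 = 46): 1 − (1 − q)^46 = 37% to 91%.
- Chance of at least one on APP13007 (m = 9): 1 − (1 − q)^9 = 9% to 37%.

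**Direction.** Assume raised-IOP rates of 3% (APP13007) and 1% (placebo) while unrescued. With post-rescue data excluded, the difference is +2.0 points. With all data and a post-rescue rate of 5% in both arms:

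- 5% / 20% rescue: (0.95 × 3 + 0.05 × 5) − (0.80 × 1 + 0.20 × 5) = 3.1 − 1.8 = +1.3.
- 10% / 40% rescue: (0.90 × 3 + 0.10 × 5) − (0.60 × 1 + 0.40 × 5) = 3.2 − 2.6 = +0.6.

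Here the exclusion makes APP13007 look worse. If the post-rescue rate were instead 10% on APP13007 and 1% on placebo, 5% / 20% rescue would give (0.95 × 3 + 0.05 × 10) − (0.80 × 1 + 0.20 × 1) = 3.35 − 1.0 = +2.35, and the exclusion would make it look better.

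**The case against.** There is a good case for the exclusion. Study drug stops at rescue and the rescue agent is the investigator's choice (protocol 5.4.1), so later readings may reflect another drug. An on-treatment IOP table is a legitimate view. Protocol 10.3.3 is silent on rescue rather than promising inclusion, observed may simply mean not imputed, and protocol 10.1 leaves analysis details to the SAP. Limiting by-visit tables to scheduled visits is ordinary practice. Unscheduled visits are one option in protocol 9.5.2 for following a raised IOP already found; if it was found at a scheduled visit before rescue, the triggering reading is already tabulated. The any-time sentence is specific and could be read as overriding both general rules.

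Most of this stands. It supports keeping a pre-rescue table, but not making it the only tabulated by-visit view. It also does not settle precedence, since SAP 11.3.1 states an exception to its exclusion only for the listing.

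A reader might go further and infer that raised-IOP readings disappear and that harm is hidden on the active arm. The documents do not support this. Every reading is listed, threshold events enter the AE tables by arm, and any larger loss would probably fall on placebo.

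**Conclusion.** The point holds as a gap between the SAP and protocol 10.3.3, and as an unresolved conflict within SAP 11.3.1. By-visit IOP and BCVA summaries depend on an efficacy-driven event after randomization, and the any-time IOP summary may disagree with the TEAE tables. To say that they will disagree would go too far: that needs at least one first threshold reading after rescue or at an unscheduled visit, and a programmer who applies the rules literally.

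The size cannot be derived from the documents. Under the assumed 5% / 20% rescue, about 9 vs 37 subjects per arm lose later readings, while fewer than one threshold subject is expected to be missing on APP13007. The direction of any distortion depends on unknown rates by arm. The analyses concerned are descriptive, and the primary efficacy analysis is not affected.

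**What to change.** Amend SAP 11, 11.3.1 and 11.3.2 before unmasking:

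1. State that the any-time threshold IOP summary uses every reading after the first dose: scheduled and unscheduled, before and after rescue. Reconcile its subject counts with the IOP TEAEs and explain any difference.
2. Tabulate by-visit IOP and BCVA twice: once with all observed data in the Safety Population, as protocol 10.3.3 plans, and once with pre-rescue data only.
3. Give the number of subjects excluded by the rescue rule, per arm and visit, in the pre-rescue version.

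The cost is SAP wording and one extra set of descriptive tables; data collection and study conduct do not change. The drawback is that the all-observed version mixes in effects of the rescue medication, which is why both versions should be shown.

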11.3.2 Best Corrected Visual Acuity

Since the BCVA endpoint will also be assessed for efficacy, this endpoint has been described in the [Section 10.2.1](#). The assessments for the study eye will be performed from Screening through EOS for safety evaluation. The assessment for the non-study eye will be performed at Screening and EOS.

The BCVA LogMAR scores and change from baseline (POD1 pre-dose) will be summarized descriptively by treatment group at each post-surgery scheduled visit through EOS for the study eye. The BCVA base LogMAR scores change from baseline will be classified as ≤ 0 , $0 < - < 0.2$ and ≥ 0.2 , which are equivalent to ≤ 0 line (visual acuity improved), $0 < - < 2$ lines, and ≥ 2 lines (visual acuity worsened). The number and percentage of subjects in each category will be tabulated at each post-surgery scheduled visit for the study eye.

The BCVA scores collected after taking rescue medication will be excluded from the summary tables for the study eye.

The BCVA LogMAR scores at Screening and EOS, and change from Screening to EOS for the non-study eye will be summarized using descriptive statistics.

All BCVA data, including data collected after taking rescue medication, will be presented in a listing.

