10.3.2 Analysis of Efficacy

All efficacy analyses and summaries will be based on assessments in the study eye for each subject.

Subjects who are rescued at any time prior to Visit 5 (POD15) will be considered as treatment failures for the primary efficacy endpoints and the relevant secondary efficacy endpoints. For subjects who discontinue from the study prior to Visit 5 (POD15), the last observation carried forward (LOCF) approach will be used to impute missing data.

For continuous secondary efficacy endpoints, the LOCF approach will also be used to impute the data at visits after subjects are rescued.

The ACC count will be graded as shown below:

Grade	0	1	2	3	4
ACC Count	0 cell	1-5 cells	6-15 cells	16-30 cells	> 30 cells

10.3.2.1 Analyses of Primary Efficacy Endpoints:

The primary efficacy analyses to compare APP13007 against placebo will be conducted on the ITT population using the Pearson Chi-square statistic. Fixed sequence testing will be employed to maintain the 2-sided alpha = 0.05. The primary analyses will first test the difference between treatments in the proportion of subjects with ACC count = 0 (Grade = 0) at POD8 (Visit 4) maintained through POD15 (Visit 5). If the test is statistically significant at the 2-sided alpha = 0.05 level in favor of APP13007, the difference between treatments in the proportion of subjects with Ocular Pain grade = 0 at POD4 (Visit 3) maintained through POD15 (Visit 5) will be tested at the two-sided alpha = 0.05 level.

To confirm the robustness of primary analysis results, sensitivity analyses, including using observed data from all subjects, will be performed. The detailed sensitivity analyses will be described in the SAP.

10.3.2.2 Analyses of Secondary Efficacy Endpoints:

Mean change-from-baseline in ACC Grade, ocular Pain Grade, ACF Grade and visual acuity at PODs 4, 8 and 15 will be analyzed using an analysis of covariance (ANCOVA). The ANCOVA model will include treatment as a fixed effect and baseline as a covariate. The rest of secondary efficacy endpoints will be analyzed using the same method described for the primary efficacy endpoints.

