6.4.2 Rescued Subjects

Any subject not responding to the study drug because of lack of efficacy at any time after randomization at Visit 2/POD1 may be rescued and placed on an appropriate alternative therapy determined by the Investigator.

The efficacy assessments performed after starting rescue medication will be excluded from the efficacy analyses.

For the primary efficacy endpoints, subjects who are rescued at any time after the first dose of study drug and before the efficacy assessments at POD15 will be considered as treatment failures (Non-responders). The same approach will be applied to derive the secondary endpoint of sustained ACF grade =0.

For both categorical and continuous secondary efficacy endpoints of ACC grade, ocular pain grade and ACF grade, the last observation carried forward (LOCF) approach will be used to impute the data for each Analysis Visit after starting rescue medication.

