6.4.3 Handling Dropouts or Missing Data

6.4.3.1 Imputation of Missing Efficacy Data

The missing data handling rule for the study eye will be applied for the efficacy endpoints.

Missing data from subjects who discontinue the study before POD15 assessments without taking rescue medication:

For subjects who prematurely discontinue the study without taking rescue medication, the LOCF approach will be used to impute the missing data. The last observation will be the last assessment value after the first dose of study drug and up to two days following the last dose of study drug.

Missing data from subjects who discontinue the study and take rescue medication before POD15 assessments:

For both categorical and continuous secondary efficacy endpoints of ACC grade, ocular pain grade and ACF grade, subjects who take rescue medication before POD15 assessments and prematurely discontinue the study, the LOCF approach will be used to impute the missing data. The last observation will be the last assessment value after the first dose of study drug and prior to starting rescue medication.

Intermittent missing data:

The likelihood of having intermittent missing data is low. For subjects with intermittent missing data for efficacy endpoints, the LOCF approach will be applied to impute the missing data, i.e., using the data collected from the most recent prior visit after the first dose of study drug.

If no data can be carried forward (i.e., missing assessments at POD 4 visit or no available post-baseline assessments), missing data will be treated as missing for the continuous endpoints and will be considered as 'Non-responder' for the categorical endpoints.

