10. EFFICACY ANALYSES

All efficacy analyses will be performed using the ITT population. In addition, analyses of the primary efficacy endpoints will be performed using the PP population as a sensitivity analysis. All efficacy analyses and summaries will be based on assessments in the study eye for each subject.

The data for subjects who are rescued at any time after the first dose of study drug and before the efficacy assessments at POD15 will be handled as described in [Sections 6.4.2](#) and [6.4.3.1](#). The data for subjects who prematurely discontinue the study without taking any rescue medications will be handled as described in [Section 6.4.3.1](#).

The Analysis Visits (PODs 4, 8 and 15) defined in [Section 6.3.5](#) will be employed in the efficacy analyses.

Baseline values for the efficacy endpoints are defined as the assessment values obtained at POD1 pre-dose.

All efficacy data will be presented in listings.

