10.2.2.2 Analysis of Continuous Endpoints of ACC, Ocular Pain, ACF and BCVA

Mean change from baseline in ACC grade, Ocular Pain grade, ACF grade and BCVA at PODs 4, 8 and 15 will be analyzed using an analysis of covariance (ANCOVA). The ANCOVA model will include treatment as a fixed effect and baseline as a covariate. The imputation for missing values for the continuous endpoints is described in [Section 6.4.3.1](#).

The values of the endpoints and change from baseline at PODs 4, 8 and 15 will be summarized by treatment group using descriptive statistics, including 95% CI for the mean of the change-from-baseline. The adjusted mean of the change from baseline and the treatment difference of adjusted means with associated 95% CI from ANCOVA will be presented. The mean change from baseline with 95% CI at PODs 4, 8 and 15 will be plotted.

In addition, the ACC grade, Ocular Pain grade, ACF grade and BCVA, and change from baseline will be summarized descriptively using the observed data only.

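### After rescue, the SAP leaves BCVA off its LOCF lists (unlike protocol 10.3.2) and keeps post-rescue study-eye BCVA out of the safety summary tables

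*SAP*

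**What the plan says.** **Efficacy.** SAP 6.4.2 sets a general exclusion: "The efficacy assessments performed after starting rescue medication will be excluded from the efficacy analyses". It then fills the gap at visits after rescue for named endpoints only, whether analysed as categories or as continuous scores. The operative wording is: "continuous secondary efficacy endpoints of ACC grade, ocular pain grade and ACF grade, the last observation carried forward (LOCF) approach will be used to impute". SAP 6.4.3.1 repeats the same three endpoints for "subjects who take rescue medication before POD15 assessments and prematurely discontinue the study". BCVA is in neither list.

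BCVA is nevertheless the fourth variable in the ANCOVA of SAP 10.2.2.2, where the sentence that sets the method begins: "Mean change from baseline in ACC grade, Ocular Pain grade, ACF grade and BCVA at PODs 4, 8 and 15 will be analyzed using". That section refers to 6.4.3.1 for imputation. SAP 10 sets the population: "All efficacy analyses will be performed using the ITT population". Protocol 10.3.2 has a broader rule: "For continuous secondary efficacy endpoints, the LOCF approach will also be used to impute the data at visits after subjects are rescued". Mean change in BCVA is one of those endpoints (protocol Table 3).

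**Safety.** SAP 11 gives the general rule, "For all safety endpoints, the observed data and scheduled visits will be used for summary statistics", and rules out imputation. SAP 11.3.2 then qualifies it for acuity: "The BCVA scores collected after taking rescue medication will be excluded from the summary tables for the study eye". Those tables include the base logMAR change classes, the worst being 0.2 or more (two lines). All BCVA values, post-rescue ones included, go into a listing. Protocol 10.3.3 plans a visual acuity summary at each visit and mentions no rescue exclusion.

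**The concern.** Rescue depends on outcome. Under protocol 9.4.1 it follows worsening or unimproved inflammation, or pain or photophobia that persists or worsens. Protocol 5.4.1 and 9.1.1.1 keep rescued subjects in the study with assessments to POD22, so the acuity data exist.

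Two separate things follow.

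1. In the ANCOVA, the SAP removes post-rescue BCVA and does not say what replaces it. Two programmers could produce different POD8 and POD15 results. If rescue is commoner on placebo and rescued eyes see worse, dropping them flatters placebo.
2. In the safety table the rule is clear, and the issue is the choice. Eyes selected for a poor course leave the two-line-loss class from the moment of rescue, in both arms.

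At stake are one secondary endpoint outside the fixed testing sequence and one safety table.

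**Working it through.** **Step 1. Which SAP rule reaches BCVA after rescue?**

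| Situation | Rule | Covers BCVA? |
|---|---|---|
| Dropout without rescue | LOCF (SAP 6.4.3.1) | Yes |
| Intermittent missing visit | LOCF (SAP 6.4.3.1) | Yes |
| Rescued, stays in study | LOCF for three named grades (SAP 6.4.2) | Not named |
| Rescued and discontinues | LOCF for the same three (SAP 6.4.3.1) | Not named |
| Any continuous secondary endpoint after rescue | LOCF (protocol 10.3.2) | Yes |

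The gap is confined to post-rescue visits. An eye rescued later still counts at its earlier visits. An eye rescued at Visit 5 keeps its POD15 value, because protocol 9.4.2 has those assessments completed before rescue medication is given.

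**Step 2. Inputs for the size.** The plan states no BCVA figure. Its only usable number is 185 per arm (175/0.95 = 184.2, rounded up). One letter is 0.02 logMAR (SAP 10.2.1). Everything else is assumed: rescue before the POD15 assessment of 5–10% on APP13007 and 15–40% on placebo, and rescued eyes worse by d = 0.1 to 0.2 logMAR at POD15.

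**Step 3. Eyes leaving the POD15 BCVA figures** = 185 × rescue rate.
- APP13007: 185 × 0.05 = 9.3; 185 × 0.10 = 18.5.
- Placebo: 185 × 0.15 = 27.8; 185 × 0.30 = 55.5; 185 × 0.40 = 74.0.

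**Step 4. Shift in the treatment difference from dropping them** = (placebo rate − active rate) × d.
- 10% v 15%, d = 0.1: 0.05 × 0.1 = 0.005 logMAR (0.25 letter).
- 5% v 30%, d = 0.1: 0.25 × 0.1 = 0.025 (1.25 letters).
- 5% v 30%, d = 0.2: 0.25 × 0.2 = 0.05 (2.5 letters).
- 5% v 40%, d = 0.2: 0.35 × 0.2 = 0.07 (3.5 letters).

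With equal rescue rates the shift is zero.

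**Step 5. Does the reading change the nominal result?** Simulation: 4,000 trials per case, 185 per arm, ANCOVA on change with baseline as covariate. There is no drug effect among non-rescued eyes. Under LOCF, rescued eyes are worse by d + 0.05, and 20% of them have nothing to carry forward. Share of trials with nominal p < 0.05, for residual SD 0.15 / 0.20:

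| Rescue, d | Rescued eyes dropped | LOCF |
|---|---|---|
| 5% v 30%, 0.1 | 4.7 / 4.6% | 49.5 / 29.8% |
| 5% v 30%, 0.2 | 4.6 / 5.6% | 84.6 / 64.1% |
| 10% v 15%, 0.1 | 4.7 / 4.7% | 6.8 / 5.1% |
| 10% v 15%, 0.2 | 5.3 / 5.2% | 10.2 / 7.7% |

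These are not false-positive rates: in these cases the arms truly differ, through rescue. They show only when the choice of reading matters.

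**Step 6. Two-line-loss table.** Assume 1% of non-rescued and 10% of rescued eyes lose two lines or more, with rescue 5% v 30%.
- Planned table: about 1% in each arm.
- All eyes, APP13007: 0.95 × 1% + 0.05 × 10% = 1.45%.
- All eyes, placebo: 0.70 × 1% + 0.30 × 10% = 3.7%.
- Not counted: 185 × 0.05 × 0.10 = 0.9 eyes on APP13007; 185 × 0.30 × 0.10 = 5.6 on placebo.

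At 10% v 15% the all-eyes rates would be 0.90 + 1.00 = 1.9% and 0.85 + 1.50 = 2.35%. The level is understated in both arms, but the difference between them barely moves.

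**The case against.** **On the ANCOVA**, the best answer is that LOCF already applies. Protocol 10.3.2 prescribes it and the SAP states no different rule for BCVA. SAP 10.2.2.2 names BCVA and sends it to 6.4.3.1, which leaves continuous data missing only where nothing can be carried forward. SAP 6.3.5 also discards late assessments in subjects who stopped dosing early; for a non-rescued subject still in the study, only the intermittent-missing rule can fill that gap. Using the rule for excluded values is therefore not far-fetched. This stands as evidence of intent. It does not close the gap: if the rule already covered post-rescue exclusions, the separate provision for three endpoints would be unnecessary.

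A reader might infer that BCVA has no imputation at all, or that the sponsor chose to analyse only never-rescued eyes. The table in Step 1 shows otherwise.

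**On the safety table**, the exclusion is explicit and matches the one for IOP in SAP 11.3.1. It avoids mixing study drug with a rescue therapy of the investigator's choosing. That is a legitimate reason for the planned table, but not for having it alone. A reader might see a conflict with protocol 10.3.2 or within the SAP. Neither holds: 10.3.2 governs efficacy, and 11.3.2 is a specific rule qualifying the general one in SAP 11. The relevant protocol text is 10.3.3, which is merely silent on rescue.

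A reader might also infer that post-rescue vision loss is hidden. It is not. Protocol 7.3.1.1 makes clinically relevant deterioration an adverse event, 8.1.1 extends reporting to rescued subjects, and SAP 11.2 tabulates TEAEs by arm. The two-line stopping rule in protocol 9.1.2 has no rescue exemption. Table n (SAP 6.2) and cumulative rescue counts at PODs 4, 8 and 15 (SAP 10.2.2.3) let a reader largely infer exclusions through POD15.

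The sizes in Steps 3 to 6 rest on assumptions, and that objection stands in full.

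**Conclusion.** The point holds in a limited form and is an optional improvement. For post-rescue visits only, the SAP omits BCVA from a rule that the protocol applies to it. This is most likely a drafting omission. Taken literally, it would bias the BCVA ANCOVA against APP13007 if rescue is commoner on placebo and rescued eyes see worse. The safety exclusion is a deliberate choice that can understate two-line loss in both arms while other safety reporting remains.

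The size cannot be fixed from the documents. Under the assumptions above, the shift in the ANCOVA difference runs from 0.005 to 0.07 logMAR. The effect on the comparison between arms is negligible when rescue rates are close and material only when they differ clearly. No primary test or conclusion changes, and the documents give no ground for calling the BCVA results invalid.

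**What to change.** 1. **SAP 6.4.2 and 6.4.3.1:** add BCVA to the endpoints with post-rescue LOCF, matching protocol 10.3.2. An eye rescued before any post-dose assessment would still have nothing to carry forward and stay missing.
2. **SAP 11.3.2:** add a supplementary version of the study-eye BCVA tables with all observed values regardless of rescue, on the same base logMAR classes. In the planned version, print the number of eyes excluded for rescue by visit and arm.
3. **Optional:** one sensitivity ANCOVA on observed BCVA including post-rescue values, following the approach of SAP 10.1.4 for the primary endpoints.

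The cost is SAP wording and extra output from data already collected; the sample size is unchanged. There are two downsides. Post-rescue values mix study drug and rescue therapy, which is why the new tables should stand beside the planned ones. LOCF freezes an early post-operative score and can overstate the deficit. In the 5% v 30%, d = 0.1 case, carried-forward eyes make up 0.24/0.94 = 25.5% of placebo and 0.04/0.99 = 4.0% of APP13007, so the shift is 0.215 × 0.15 = 0.032 logMAR against 0.025 with all eyes observed. That difference is the argument for item 3.
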